6.2.1.1.1 Adverse Events of Special Interest

The following AESIs will be reported using the same process as for AEs:

Injection site reactions

Injection site reactions will be observed after study drug administration and assessed based on Common Terminology Criteria for Adverse Events (CTCAE) v5.0. All AEs related to injection site reaction including erythema, itching, hemorrhage, pain, and swelling will be reported.

Hypersensitivity/allergic reactions

All AEs related to hypersensitivity and allergic reactions occurring within 24 hours after the study drug administration will be reported.

Infection

All AEs related to infection including TB, sepsis, and other opportunistic infections will be reported.

Malignancy

All AEs related to malignancy including but not limited to the following: hepatosplenic T-cell lymphoma, leukemia, lymphoma, melanoma, and Merkel cell carcinoma.

6.2.1.1.2 Serious Adverse Events

An SAE is defined as any untoward medical occurrence that at any dose:

- Results in death
- Is immediately life-threatening
- Requires in-patient hospitalization or prolongation of existing hospitalization
- Results in persistent or significant disability/incapacity
- Is a congenital anomaly/birth defect

Important medical events that may not result in death, be life threatening, or require hospitalization may be considered SAEs when, based upon appropriate medical judgment, they may jeopardize the subject or may require medical or surgical intervention to prevent one of the outcomes listed in this definition. Examples of such medical events include allergic bronchospasm requiring intensive treatment in an emergency room or at home, blood dyscrasias or convulsions that do not result in in-patient hospitalization, or the development of drug dependency or drug abuse.

6.2.1.1.3 Suspected Unexpected Serious Adverse Reactions

A suspected unexpected SAE is defined as an event of which the nature or severity is not consistent with the applicable product information (e.g., IB) for an unapproved investigational product or the label (e.g., package insert, SmPC, or prescribing information) for an approved product. Assessment of expectedness will be made with the use of the IB and the SmPC. Therefore, if a treatment-related SAE occurs and it was not mentioned in the applicable product information, then it will be reported as a SUSAR (Suspected Unexpected Serious Adverse Reaction).

6.2.1.2 Eliciting and Documenting Adverse Events

Adverse events will be assessed from the time the ICF is signed and until the end of the subject's participation in the study. All AEs will be followed until resolution or improvement to baseline, death, confirmed by the investigator that no further improvement could be expected, no more collection of clinical or safety data, or final database closure. Adverse events of special interest (e.g., injection site reactions, hypersensitivity/allergic reactions, infections, and malignancies) will be closely monitored.

Subjects will be asked a standard question to elicit any medically related changes in their well-being. They will also be asked if they have been hospitalized, had any accidents, used any new medications, or changed concomitant medication regimens (both prescription and OTC medications).

In addition to subject observations, AEs will be documented from any data collected on the AE page of the eCRF (e.g., laboratory values, physical examination findings, ECG changes) or other documents that are relevant to subject safety.

6.2.1.3 Reporting Adverse Events

All AEs reported or observed during the study will be recorded in both the source documents and on the AE page of the eCRF. Information to be collected includes drug treatment, type of event, time of onset, action taken with study drug, investigator-specified assessment of

severity and relationship to study drug, time of resolution of the event, seriousness, as well as any required treatment or evaluations, and outcome.

Adverse events resulting from concurrent illnesses, reactions to concurrent illnesses, reactions to concurrent medications, or progression of disease states will also be reported. Adverse events will be recorded according CTCAE v5.0. The Medical Dictionary for Regulatory Activities (MedDRA) will be used to code all AEs.

Any medical condition that is present at the time that the subject is screened but does not deteriorate will not be reported as an AE. However, if it deteriorates at any time during the study, it will be recorded as an AE.

The investigator's assessment of an AE's relationship to study drug is part of the documentation process, but it is not a factor in determining what is or is not reported in the study. If there is any doubt as to whether a clinical observation is an AE, the event will be reported.

[figure not shown]
The severity and the relationship or association of the study drug in causing or contributing to the AE will be characterized as defined in [Sections 6.2.1.5](#) and [6.2.1.6](#), respectively.

Adverse events (and SAEs) should be reported until the EOS visit regardless of the relationship to the study drug. After the EOS visit, serious adverse drug reactions will be reported to CELLTRION, Inc. or its designee.

6.2.1.4 Reporting Serious Adverse Events

Any AE considered serious by the investigator or which meets SAE criteria ([Section 6.2.1.1.2](#)) must be reported to [REDACTED] PVG and the sponsor immediately (within 24 hours after the study center staff first notices about the event).

The following contact information is to be used for SAE reporting:

Data entry should be completed in the remote data capture system by the investigator within 24 hours of awareness of an SAE. In the event that this is not possible (e.g., system failure or access problems), the study center should complete an SAE report form and fax (or e-mail) it

to [REDACTED] PVG within 24 hours of awareness of the event. The remote data capture system should be updated as soon as it is available. If the subject is hospitalized during an SAE or because of an SAE, a copy of the hospital discharge summary will be faxed (or e-mailed) to [REDACTED] PVG as soon as it becomes available. Withdrawal from the study and all therapeutic measures will be at the discretion of the principal investigator or sub-investigator.

CELLTRION, Inc. or its designee is responsible for reporting relevant SAEs to the competent authority, other applicable regulatory authorities, and participating investigators, in accordance with European Clinical Trials Directive (Directive 2001/20/EC), International Council for Harmonisation (ICH) guidelines, and/or local regulatory requirements.

CELLTRION, Inc. or its designee is responsible for reporting fatal or life-threatening SUSARs, (expedited reports) to the regulatory agencies and competent authorities by telephone or fax within 7 calendar days after being notified of the event. CELLTRION, Inc. or its designee should report other relevant SAEs associated with the use of the study drug to the appropriate competent authorities (according to local guidelines), investigators, and central ethics committees by a written safety report within 15 calendar days of notification.

Adverse events associated with hospitalization or prolongations of hospitalization are considered as SAEs. Any initial admission (even if less than 24 hours) to a healthcare facility meets these criteria. Admission also includes transfer within the hospital to an acute/intensive care unit (e.g., from the psychiatric wing to a medical floor, from medical floor to a coronary care unit, from neurological floor to a TB unit).

Hospitalization or prolongation of hospitalization in the absence of a precipitating clinical AE is not in itself an SAE. Examples include the following:

- Admission for treatment of a pre-existing condition not associated with the development of a new AE or worsening of the pre-existing condition (e.g., for work-up of persistent pre-treatment laboratory abnormality)
- Social admission (e.g., subject has no place to sleep)
- Administrative admission (e.g., for yearly physical examination)
- Protocol-specified admission during a study (e.g., for a procedure required by the study protocol)
- Optional admission not associated with a precipitating clinical AE (e.g., for elective cosmetic surgery)

- Hospitalization for observation without a medical AE
- Hospitalization purely for convenience (e.g., for easier performance of study assessments)
- Pre-planned treatments or surgical procedures; these should be noted in the baseline documentation for the entire protocol and/or for the individual subject

6.2.1.5 Assessment of Severity

The severity, or intensity, of an AE refers to the extent to which an AE affects the subject's daily activities. The severity of the AE will be graded based on the CTCAE v5.0, based on the following general guidelines (a semicolon indicates "or" within each description):

Grade 1: Mild AE (minor; no specific medical intervention; asymptomatic laboratory findings only; radiographic findings only; marginal clinical relevance)

Grade 2: Moderate AE (minimal intervention; local intervention; noninvasive intervention [packing, cautery])

Grade 3: Severe and undesirable AE (significant symptoms requiring hospitalization or invasive intervention; transfusion; elective interventional radiological procedure; therapeutic endoscopy or operation)

Grade 4: Life-threatening or disabling AE (complicated by acute, life-threatening metabolic or cardiovascular complications such as circulatory failure, hemorrhage, or sepsis; life-threatening physiological consequences; need for intensive care or emergent invasive procedure; emergent interventional radiological procedure, therapeutic endoscopy, or operation)

Grade 5: Death related to AE

Changes in the severity of an AE will be documented to allow an assessment of the duration of the event at each level of severity to be performed. If an AE upgrades in severity or, changes from non-serious to serious, a new AE needs to be reported. If an AE downgrades in severity, it should not be reported as a new AE. Adverse events characterized as intermittent do not require documentation of onset and duration of each episode.

6.2.1.6 Assessment of Causality

As discussed in [Section 6.2.1.3](#), the investigator's assessment of an AE's relationship to study drug is part of the documentation process, but it is not a factor in determining what is or is not

reported in the study. If there is any doubt as to whether a clinical observation is an AE, the event will be reported.

The relationship or association of CT-P17 or Humira in causing or contributing to the AE will be characterized using the following classification and criteria:

Unrelated: This relationship suggests that there is no association between the study drug and the reported event.

Possible: This relationship suggests that treatment with the study drug caused or contributed to the AE, i.e., the event follows a reasonable temporal sequence from the time of drug administration or follows a known response pattern to the study drug, but could also have been produced by other factors.

Probable: This relationship suggests that a reasonable temporal sequence of the event with drug administration exists and, based upon the known pharmacological action of the drug, known or previously reported adverse reactions to the drug or class of drugs, or judgment based on the investigator's clinical experience, the association of the event with the study drug seems likely. The event disappears or decreases on cessation or reduction of the dose of study drug.

Definite: This relationship suggests that a definite causal relationship exists between drug administration and the AE, and other conditions (concurrent illness, progression/expression of disease state, or concurrent medication reaction) do not appear to explain the event. The event reappears or worsens if the study drug is re-administered.

6.2.2 Other Safety Assessments

6.2.2.1 Immunogenicity Assessment

Immunogenicity of CT-P17, US-licensed Humira, and EU-approved Humira will be assessed at the time points indicated in the schedule of assessments ([Table 10-1](#)).

The immunogenicity of CT-P17 and reference drugs will be assessed at baseline and post-treatment serum measures by a validated immunoassay.

Samples will be drawn before dosing of study drug, at the same time as the clinical laboratory tests, where applicable. If the blood sample was unable to be analyzed or was missing, some blood samples collected for PK assessment at the same time point could be used for

immunogenicity assessment. Analysis of the samples will be performed at the central laboratory.

6.2.2.2 Injection Site Reaction

Injection site reactions will be assessed 30 minutes (± 10 minutes) after study drug administration, as specified in the schedule of assessments ([Table 10-1](#)).

Details will be recorded in both the source documents and the eCRF.

6.2.2.3 Hypersensitivity/Allergic Reactions Monitoring

Hypersensitivity/allergic reactions will be assessed by additional ECG and vital sign monitoring (including systolic and diastolic blood pressure, heart rate, respiratory rate, and body temperature), to monitor for possible hypersensitivity/allergic reactions, at the time points indicated in the schedule of assessments ([Table 10-1](#)).

In addition, hypersensitivity/allergic reactions will be monitored by routine continuous clinical monitoring. In case of hypersensitivity, emergency medication and equipment, such as adrenaline, antihistamines, corticosteroids, and respiratory support including inhalational therapy, oxygen, and artificial ventilation will be available and an ECG can be performed.

6.2.2.4 Vital Signs, Weight, and Height

Vital signs will be measured at the time points indicated in the schedule of assessments ([Table 10-1](#)). The following vital signs will be measured: systolic and diastolic blood pressure (mmHg), heart rate (beats per minute), respiratory rate (breaths per minute), and body temperature ($^{\circ}\text{C}$). Blood pressure and heart rate measurements will be performed after the subject has been resting for at least 5 minutes. All measurements will be documented at each visit. Details will be recorded in both the source documents and the eCRF.

Vital sign measurements will also be monitored before and after study drug administration as part of the hypersensitivity monitoring ([Section 6.2.2.2](#)).

Body weight and height will be measured according to the schedule of assessments ([Table 10-1](#)).

6.2.2.5 Electrocardiogram

Single 12-lead ECGs will be obtained after the subject has been in the supine position for at least 5 minutes at the time points indicated in the schedule of assessments ([Table 10-1](#)).

Electrocardiograms for hypersensitivity monitoring will be performed at 3 hours (± 30 minutes) after the administration of study drug and additional ECGs can be performed if the subject experiences cardiac symptoms. Either 3-lead or 12-lead ECGs can be used for hypersensitivity monitoring. If, following ECG review by the investigator, there are any ECG findings that would indicate cardiac insufficiency or QT prolongation, the subject will be referred to a cardiologist and the event will be recorded in the source documents and the eCRF. Regardless of the ECG result, further evaluation with a cardiologist can be performed depending on the investigator's discretion.

6.2.2.6 Physical Examinations

A standard physical examination will be performed at the time points indicated in the schedule of assessments ([Table 10-1](#)).

The physical examination includes an assessment of general appearance and a review of systems. Investigators will evaluate subjects for any indication of infections and injection site reactions in accordance with the investigator's medical judgment.

Information about the physical examinations will be recorded by the investigator or designee in both the source documents and the eCRF. Any abnormalities will be recorded in the source documents. Clinically significant findings and illnesses reported after the start of the study that meet the definition of an AE will be recorded as such in the source documents and eCRF.

6.2.2.7 Tuberculosis Assessments

At Screening, subjects with active TB, latent TB (defined as a positive result for IGRA with no active lesion in examination of chest X-ray without any sign or symptom of TB), a history of TB, or had close contact with a person with active TB within 8 weeks prior to administration of the study drug (Day 1) will not be enrolled in the study.

Subjects will be monitored for the clinical signs and symptoms of TB throughout the study and until the EOS, as specified in the schedule of assessments ([Table 10-1](#)); IGRA and chest X-ray can be performed at the investigator's discretion based on the judgment on the signs and symptoms of TB monitoring.

6.2.2.7.1 Chest X-ray

A chest X-ray (both posterior–anterior and lateral views) will be performed at Screening as indicated in the schedule of assessments ([Table 10-1](#)). The results will be read by a qualified radiologist to specifically look for evidence of current or previous active or latent TB. The findings will be recorded in both the source documents and eCRF.

Radiographic findings suggestive of healed TB or active TB may include, but are not limited to, pulmonary nodules, fibrotic scars, calcified granulomas, upper lobe infiltrates, cavitations, and pleural effusions. The chest X-ray will be available to the investigator for review and any abnormal findings will be discussed with the medical monitor and sponsor before the administration of the study drug (Day 1).

6.2.2.7.2 Interferon- γ Release Assay

An IGRA will be performed at Screening and at the EOS indicated in the schedule of assessments ([Table 10-1](#)).

If the result of IGRA is indeterminate at Screening, retest will be allowed only once during the Screening period. If the repeated IGRA result is again indeterminate or positive, the subject will be excluded from the study. If the repeated IGRA result is negative, the subject may be included in the study.

If the result of the IGRA is indeterminate after administration of the study drug, one retest will be possible. If the repeated IGRA test result is again indeterminate, the investigator will discuss and agree with the sponsor or its designee the next action to be taken.

If the result of the IGRA is positive during the study, subjects will be referred to the clinicians immediately to be investigated for the presence of active TB based on medical history and any clinical signs and symptoms including chest X-ray result.

The analysis will be performed at the local laboratory.

6.2.2.8 Pregnancy

A serum pregnancy test (β -human chorionic gonadotropin) will be performed on women of childbearing potential at Screening and EOS, as indicated in the schedule of assessments ([Table 10-1](#)). A urine pregnancy test will be performed on women of childbearing potential on Day -1. Only subjects with negative results for both serum pregnancy test at Screening and urine pregnancy test on Day -1 can be enrolled in the study.

Throughout the study, a urine pregnancy test will be performed when there is any possibility of pregnancy, and a confirmatory serum pregnancy test will be performed if a urine pregnancy test result is positive.

In an event of unexpected pregnancy during study participation and for 5 months after administration of the study drug, the subjects will be counselled to inform the investigator. If a female subject or the partner of a male subject becomes pregnant, the pregnancy must be

reported to CELLTRION, Inc. and [REDACTED] PVG within 24 hours of the study center's knowledge of the pregnancy while confirmation is pending. The study center must complete the supplied pregnancy form (female subject or partner of a male subject) and return it to CELLTRION, Inc. and [REDACTED] PVG within 24 hours after acquisition of the consent for the pregnancy form.

Pregnant subjects or the pregnant partners of male subjects will be followed until the end of the pregnancy (e.g., delivery, stillbirth, miscarriage) and the mother and the baby will be followed for 1 year after the birth, provided consent is obtained. Pregnancy alone will not be regarded as an AE unless there is a suspicion that the study drug may have interfered with the effectiveness of a contraceptive medication. Elective abortions without complications should not be handled as AEs, unless they are therapeutic abortions. Hospitalization for normal delivery of a healthy newborn should not be considered as SAE. Any SAE that occurs during pregnancy (e.g., maternal serious complications, therapeutic abortion, ectopic pregnancy, stillbirth, neonatal death, congenital anomaly, birth defect) must be reported within 24 hours in accordance with the procedure for reporting SAEs ([Section 6.2.1.4](#)).

6.2.3 Hepatitis B, Hepatitis C, Human Immunodeficiency Virus and Nontreponemal Test

At Screening, HBsAg, HBsAb, and HBcAb (total or IgG) will be assessed in all subjects (mandatory) as specified in the [Table 6-1](#). If a subject has HBsAg negative, HBsAb negative or positive, and HBcAb (IgG or total) positive, a hepatitis B virus (HBV) DNA test will be performed at Screening and its result will be used to determine the eligibility.

Table 6-1 Eligibility Based on Serology Markers for Hepatitis B Infection

Test results				Eligibility
HBsAg	HBsAb	HBcAb	HBV DNA	
+	+/-	+/-	Not applicable	Not eligible
-	+/-	+	+	Not eligible
			-	Eligible
-	+/-	-	Not applicable	Eligible

Abbreviations: HBcAb, hepatitis B core antibody; HBsAb, hepatitis B surface antibody; HBsAg, hepatitis B surface antigen; HBV, hepatitis B virus.

As specified in [Table 6-1](#), the subject enrollment will be based on the test results.

Hepatitis C antibody (HCAb) test, HIV (HIV-1 and HIV-2) tests and nontreponemal test will be performed at Screening in all subjects (mandatory). If any of those test results is positive, the subject will be excluded from the study.

6.2.4 Clinical Laboratory Testing

Blood and urine samples for clinical laboratory assessments will be collected at the time points indicated in the schedule of assessments ([Table 10-1](#)) and will be prepared using standard procedures. The analysis will be performed at the local laboratory.

The following clinical laboratory assessments will be performed:

Hematology: Hematocrit, hemoglobin, red blood cell (RBC) count, white blood cell (WBC) count with differential, absolute neutrophil count, platelets

Serum Chemistry: Albumin, alkaline phosphatase (ALP), alanine aminotransferase (ALT), aspartate aminotransferase (AST), blood urea nitrogen (BUN), calcium, chloride, total cholesterol, creatine phosphokinase (CPK), creatinine, creatine kinase-myocardial band isoenzyme (CK-MB), creatinine clearance (CrCl) [estimated by Modification of Diet in Renal Disease formula], C-reactive protein, gamma glutamyl transferase (GGT), glucose, lactate dehydrogenase (LDH), magnesium, potassium, sodium, total bilirubin, total protein, uric acid, direct bilirubin, triglycerides, inorganic phosphorus, high-density lipoprotein (HDL) cholesterol, Troponin I

Urinalysis:	Color, pH, specific gravity, ketones, protein, glucose, bilirubin, nitrite, urobilinogen, occult blood, and microscopic examination
Serology:	Anti-HIV (HIV-1 and HIV-2) antibodies, hepatitis B surface antigen (HBsAg), hepatitis B surface antibody (HBsAb), hepatitis B core antibody (HBcAb [total or IgG]), HBV DNA, hepatitis C antibody (HCAb), nontreponemal (e.g., Rapid Plasma Reagins) tests
Urine drug, alcohol, and nicotine:	Tetrahydrocannabinol (THC) (or other metabolite to screen cannabis), opiates (OPI), cocaine (COC), methamphetamine (MET), barbiturates (BAR), and benzodiazepines (BZO). The history of drug abuse, alcohol and nicotine will be checked by medical history taking by the Investigator during the Screening period and Baseline (Day -1).

Creatinine clearance will be calculated using serum creatinine level only at screening for inclusion. The result will be considered for inclusion by the discretion of the investigator, and it will be recorded on source document and eCRF.

Any value outside the normal range will be flagged for the attention of the investigator or the sponsor at the study center. The investigator will indicate whether or not the value is clinically significant. If the result of the screening is indicated as clinically significant abnormal value, the subject will NOT be allowed into the study without permission of the sponsor. However, retest is permitted only once during screening period by the Investigator's judgment. Additional testing during the study may be performed if medically indicated. If a clinically significant abnormality defined as per [Section 6.2.1](#) is found in the samples taken after dosing, during the study, and/or at the EOS visit, it should be recorded as an AE and the study subject will be followed up until the test(s) has (have) normalized or stabilized.

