4.1 Inclusion Criteria

Subjects who meet all of the following criteria will be considered eligible to participate in the clinical study:

1. Healthy male or female subjects, between the ages of 19 and 55 years, both inclusive (healthy is defined as no clinically relevant abnormalities identified by a detailed medical history, full physical examination, including blood pressure and heart rate measurement, 12-lead ECG, and clinical laboratory tests prior to the administration of the study drug).
2. Subject with C-reactive protein ≤ 1.5 times the upper limit of normal (ULN).
3. Subject has adequate liver function as determined by the following results:
 - Serum alanine aminotransferase (ALT) and aspartate aminotransferase (AST) $\leq 1.5 \times$ ULN and,
 - Total bilirubin $\leq 1.5 \times$ ULN.
4. Subject is informed and able to understand the full nature and purpose of the study, including possible risks and side effects, and is given ample time and opportunity to read and understand this information. The subject has the ability and agrees to cooperate with the investigator and must sign and date the written informed consent prior to performing any of the screening procedures.
5. BMI between 18.0 and 29.9 kg/m², both inclusive, when rounded to the nearest tenth
6. Subject and their partner of childbearing potential must agree to use a highly effective method of contraception as specified in [Section 5.8.2](#), throughout the study and for 5 months after the administration of assigned treatment. A man or woman is of childbearing potential if, in the opinion of the investigator, he or she is biologically capable of having children and is sexually active. Male and female subjects and their partners who have been surgically sterilized for less than 24 weeks prior to the date of informed consent must agree to use any medically acceptable methods of contraception. Menopausal

females must have experienced their last period more than 1 year prior to the date of informed consent to be classified as not of childbearing potential.

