5.1 Method of Assigning Subjects to Treatment Arms

An interactive voice response system (IVRS) or an interactive web response system (IWRS) will be used for the randomization. Enrolled subjects who meet all of the inclusion and none of the exclusion criteria will be randomly assigned in a 1:1:1 ratio into one of three treatment arms. Randomization numbers will be assigned before administration of the study drug on Day -1. As it is known that the body weight and gender are potential impact factors on pharmacokinetic profile, the randomization to treatment assignment will be stratified by body weight (≥ 80 kg vs. <80 kg) as measured on Day -1, gender (male vs. female) and study center, considering that it is a multi-center study.

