6.2.1 Adverse Events

6.2.1.1 Definitions of Adverse Events

The investigator is responsible for reporting all AEs that are observed or reported during the study, regardless of their relationship to study drug or their clinical significance.

An AE is defined as any untoward medical occurrence associated with the use of a drug in humans, whether or not considered drug related. Subjects will be instructed to contact the investigator at any time after the ICF was signed if any symptoms develop.

A treatment-emergent AE (TEAE) is defined as any event not present before exposure to study drug or any event already present that worsens in severity or frequency after exposure to study drug. This includes any occurrence that is new in onset or aggravated in severity or frequency from the baseline condition; abnormal results of diagnostic procedures including laboratory test abnormalities are considered AEs if they fulfill the following:

- Result in discontinuation from the study
- Require treatment or any other therapeutic intervention
- Require further diagnostic evaluation (excluding a repetition of the same procedure to confirm the abnormality)
- Are associated with clinical signs or symptoms judged by the investigator to have a significant clinical impact

Medical interventions such as surgery, diagnostic procedures, and therapeutic procedures are not AEs but the action taken to treat the medical condition. They should be recorded as

treatment(s) of the AEs. The event term of primary cause should be recorded and reported instead of the term of surgery, diagnostic procedure, or therapeutic procedure.

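### Section 6.2.4 is worded so that the sponsor can permit entry despite a clinically significant screening laboratory value, which conflicts with inclusion 1 and the randomisation rule

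*Protocol*

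**What the plan says.** **Section 6.2.4 of the protocol** gives the first judgement on an out-of-range value to the investigator: "The investigator will indicate whether or not the value is clinically significant". For a screening result judged to be a "clinically significant abnormal value, the subject will NOT be allowed into the study without permission of the sponsor". The next sentence adds that a "retest is permitted only once during screening period", at the investigator's judgement. Permission is not tied to the outcome of that retest, and no criteria for giving it are stated.

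**Section 4.1, inclusion 1** requires a healthy subject, where "healthy is defined as no clinically relevant abnormalities identified by" a set of assessments that includes "clinical laboratory tests prior to the administration of the study drug".

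**Section 5.1** states the randomisation rule: "Enrolled subjects who meet all of the inclusion and none of the exclusion criteria will be randomly assigned". Section 5.2 and SAP section 5.4 repeat it. None of the three mentions sponsor permission.

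**Related safeguards:**
- Section 3.2.1, and footnote 1 of Table 10-1, make a volunteer whose repeat screening test is again unsuitable a screen failure.
- Section 3.2.2 and Table 10-1 schedule laboratory tests and a recheck of the criteria on Day -1. A volunteer found ineligible that day is a screening failure.
- Section 9.2.1 requires exact adherence to the protocol. Section 9.2.2 says that a breach of the eligibility criteria can be a significant deviation, which leads to withdrawal.

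**The concern.** A volunteer whose screening value the investigator has marked clinically significant would appear to fail inclusion 1, and so could not be randomised under section 5.1. Section 6.2.4 nevertheless describes a route into the study for that volunteer if the sponsor agrees. A site following 6.2.4 and a site following 4.1 could reach opposite decisions on the same result.

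What is at stake is protection of volunteers. Section 1.4 reports no earlier clinical study of CT-P17, and section 1.6 says no therapeutic benefit is intended for the subjects. The entry criteria are therefore a main safeguard, and a waiver by the party that runs the trial should not be open by implication.

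**Working it through.** No alpha, power, variance or margin enters this point. The check is a comparison of texts, with one count to show its scope.

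**Step 1: what each text does with the same volunteer.** Take a volunteer with one screening laboratory value that the investigator marks clinically significant.

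| Text | Result | Sponsor exception? |
|---|---|---|
| Protocol 4.1, inclusion 1 | Not healthy as defined, so not eligible | None |
| Protocol 5.1 and 5.2; SAP 5.4 | Not randomised | None |
| Protocol 3.2.1 | Screen failure if a repeat is again unsuitable | None |
| Protocol 3.2.2 | Screening failure if found ineligible on Day -1 | None |
| Protocol 6.2.4 | Kept out unless the sponsor permits entry | Yes, without criteria |

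**Step 2: do the two terms differ?** Inclusion 1 speaks of clinical relevance and 6.2.4 of clinical significance. The protocol draws no distinction between them. Its only definition of the second term is for samples taken after dosing ("If a clinically significant abnormality defined as per" section 6.2.1). The conditions listed there are discontinuation from the study, "Require treatment or any other therapeutic intervention", further diagnostic work-up, or association with signs or symptoms of significant clinical impact. A screening value of that kind would be hard to call not clinically relevant. That is an inference, because the definition is not applied to screening samples.

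**Step 3: does the retest resolve the conflict?** No. The retest is optional and permission does not depend on it. If a repeat is done and is again unsuitable, section 3.2.1 already requires screen failure.

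**Step 4: does Day -1 resolve it?** In part. Every volunteer has laboratory tests that day, and section 3.2.2 has no override. The permission sentence refers to the screening result, so it does not on its face reach a Day -1 value. However, footnote 4 of Table 10-1 requires the criteria to be confirmed before Day -1 and then rechecked. The decision on the screening value therefore comes first, and 6.2.4 is the text that speaks to it.

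**Step 5: how the rest of the protocol writes such rules.** Section 6.2.3 excludes a volunteer with a positive hepatitis C antibody, HIV or nontreponemal test. Exclusion 4 excludes a volunteer whose repeat interferon-γ release assay is indeterminate or positive. Neither leaves room for permission.

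**Step 6: scope.** Section 6.2.4 lists 6 hematology items (white cell count with differential counted once) and 27 serum chemistry items: 6 + 27 = 33. Inclusion 2 and 3 set numeric limits for 4 of them (C-reactive protein, ALT, AST, total bilirubin): 33 − 4 = 29. For those 29 items entry rests on clinical judgement, and there the permission sentence matters most. Urinalysis is not in this count. The count describes the tests concerned and says nothing about how many volunteers are affected.

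**The case against.** The strongest reply is that the sentence restricts entry and does not grant it. It makes sponsor permission necessary, without saying that permission is enough. On that reading it adds a second reviewer, so that an investigator cannot admit a flagged volunteer alone, and inclusion 1 still has to be met. The permission would then have a use: a volunteer flagged once, whose retest is acceptable, could meet inclusion 1 and still need sponsor sign-off. It can also be said that 6.2.4 flags a single value, whereas inclusion 1 judges health from history, examination, ECG and laboratory tests together.

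Part of this stands. The sentence may well have been meant as an extra check. But permission is attached to the flagged result, not to an acceptable retest, and the text does not add that all criteria must still be met. The harmonising reading has to supply both conditions.

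The safeguards also stand as limits on the risk. A reader might infer that a volunteer with, say, a low platelet count at Screening could be dosed without the count being checked again. The documents do not support that, because the Day -1 tests and recheck apply to everyone. A reader might also infer that nothing indicates which rule governs. That goes too far: sections 9.2.1 and 9.2.2 point towards the eligibility criteria. Even so, section 9.2.2 describes a deviation as something unintended or unanticipated, and entry by advance permission fits that poorly. Exclusion 15 lets the investigator exclude on laboratory results, and exclusion 2 adds a judgement on cardiac function from laboratory results. Both rest on discretion, and neither cancels the permission wording.

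**Conclusion.** The point holds as a conflict of wording with a bearing on volunteer safety, and it is minor. Section 6.2.4, read naturally, leaves a route by which the sponsor can admit a volunteer whom inclusion 1 and the randomisation rule would keep out. Day -1 testing, the screen-failure rule and section 9.2 reduce the practical risk without closing that route.

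The conclusion rests on two readings: that barring entry without permission implies entry with it, and that a clinically significant value is also a clinically relevant one. The protocol says nothing against either.

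The size in volunteers is unknown, since no rate of clinically significant screening values is given. The documents do not show that permission was ever granted. SAP sections 5.5.2 and 6.3 record no major protocol deviations at the data review meeting. That does not settle the matter, because an entry allowed by 6.2.4 might not have been classed as a deviation. No effect on the pharmacokinetic comparison is claimed, and none should be inferred.

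**What to change.** In section 6.2.4, replace the permission and retest sentences with:

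> A clinically significant abnormal screening result may be retested once during the screening period at the investigator's judgement; if it is not retested, or the repeat is again clinically significant, the subject will be screen failed. The sponsor may not waive an eligibility criterion.

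If the sponsor wants to keep its review, it can be added only as a further check on volunteers whose retest is acceptable and who meet all criteria.

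The cost is one wording change, made by amendment with ethics board approval as section 9.2.1 requires. Endpoints, sample size and analysis are unaffected, and the text then agrees with sections 3.2.1, 4.1 and 5.1. The downside is that a few volunteers the sponsor would have admitted become screen failures. The single rescreen in section 4.3 stays open to them.
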